**Randomization:**

Each patient will be randomized to one of two groups: intrathecal morphine with intraoperative periarthicular injection using a "joint cocktail" (treatment group) and intrathecal morphine with a placebo injection (placebo group) for perioperative pain management. A randomization schedule created by the pharmacy prior to the study will be used to determine to which treatment group each patient will be assigned. The pharmacists will prepare either injection and transport to the OR during each patient's procedure. The treatment group will receive an injection of 50 mL of 0.5% ropivacaine, 0.8 mL (0.1mg/mL) clonidine, 1 mL (30 mg/mL) ketorolac, 0.5 mL (1 mg/mL) epinephrine, and 47.7 mL 0.9% saline for a total volume of 100 mL. The patients in the placebo group will receive 100 mL of 0.9% saline.

**Preoperative Intervention:**

HM20004125 [name]  
Do Intraoperative Periarthicular Injections Improve Postoperative Pain Control in Patients Receiving Duramorph? A Prospective, Double Blinded, Randomized Controlled Trial

## Project Details

1. \* Select all of the following types of interventions that apply to this study (selections will branch):

- Social/Behavioral interventions or experimentation / Tasks / Environmental manipulations
- Deception (misleading participants through false or incomplete information)
- Drug(s) / Biologics / Supplement(s) / Other Compounds (Investigational products or products whose administration is dictated by the study protocol and not per the physician's clinical judgment)
- Placebos
- Safety and/or effectiveness evaluation of Bio-Medical Device(s), including in-vitro diagnostic devices/assays, mobile medical apps, software functions, and HUDs used in clinical investigations
- Washout Periods
- Expanded Access - Treatment Use of an Investigational Product
- Medical or Surgical Procedures (eg: physical exam, clinical procedures, scans, etc)
- Specimen/biological sample collection
- None of the Above

2. \* Describe the nature/content of the placebo and justify the use of placebo control.

Some surgeons still do NOT use periarthicular injections routinely during total knee arthroplasty. Given that patients already receive multiple different interventions as a part of their postoperative pain management plan, the use of these injections may not have an additive value. In order to obtain objective data regarding the periarthicular injections' impact on postoperative analgesia, we will need to exclude it from one group for a true comparison.

3. \* Select all of the following types of interactions that apply to this study (selections will branch):

- Surveys / Questionnaires /Written responses to questions (including data entry)
- Active Internet data collection (i.e. using the internet to interact or intervene directly with research participants)
- Interviews / Focus Groups / Verbal responses to questions
- Audio / Video recording or photographing participants
- Observations
- Passive Internet data collection (i.e. passively observing online behavior)
- Educational Settings/Assessments/Procedures
- None of the Above

4. \* Select all types of secondary information and/or specimens that apply to this study (selections will branch):  
See the help text for definitions.

- Individually Identifiable Health Information (PHI or RHI)
- Secondary data/specimens NOT from a research registry or repository
- Information/specimens from a research registry or repository (Usage Protocol)
- Information/specimens originally collected for a previous research study
- Publicly available information/specimens
- Government-generated or collected information that was or will be obtained for nonresearch activities [only applicable to research conducted by or on behalf of a Federal department or agency]
- No secondary data/specimens will be used

## Secondary Data/Specimen Details

1. Describe the source(s) and nature of the information/specimens being obtained. This response should:

- Identify where the data/specimens will come from (e.g., another researcher's registry, pathology lab, commercial source, medical records, etc.); and
- List what types of specimens will be obtained (when applicable); and/or
- List all data elements that will be obtained (when applicable). A data collection form or other documentation may be uploaded and referenced here.

The data being collected includes pain medicine administered for the first 48 hours after surgery. There is a data collection form uploaded in documents. Visual analogue scores are not being collected any longer due to poor reliability.

2. Describe whether any agreement exists between you and data/specimen provider that states you will never have access to the ability to identify the participants (i.e. access to identifiers or the code key) and that you will not attempt to re-identify individuals.

Each subject has a subject number that is being assigned by RedCap (the index number) used as a code. This number is used on the data collection form. Once all data is collected and entered into RedCap this form will be destroyed. Once all data is collected and analyzed all identifiers will be removed from RedCap.

The patient identifiers are in redcap and will not be used in any way that would identify the patient by name. The data will be used in aggregate when reporting the results.

3. When the information/specimens were originally collected, did individuals provide consent for secondary research use of their data/specimens (i.e. consent to another research study or to a research registry)?

Yes

No

HM20004125 [name]  
Do Intraoperative Periarthicular Injections Improve Postoperative Pain Control in Patients Receiving Duramorph? A Prospective, Double  
Blinded, Randomized Controlled Trial

## Contingency Plan

This page will be used by the IRB in the event that an institution-wide emergency situation arises that requires contingency plans.

A contingency plan describes the alternative procedures that a study would want to use in case of an emergency that prevented normal study activities from occurring. It is a form of adaptive protocol. It enables the VCU IRB to quickly approve alternative study activities along with criteria for when those activities would or would not be put into effect. For example, in 2020, some studies had a COVID-19 Contingency Protocol approved that described alternative remote procedures that they would switch to whenever the University restricted in-person research activities.

In all studies, investigators are strongly encouraged to plan prospectively and build flexibilities into their regular protocols (regardless of whether an emergency situation exists) as well as think about what they would do in an emergency situation. For example, windows for timed study visits, ranges instead of exact values, flexibilities in inclusion criteria, etc. Flexibility and adaptations that are built into the protocol will reduce the number of changes that have to be submitted to the IRB and should reduce the number of incidents of deviations and noncompliance by investigators.

Further instructions and smartform questions on this page will be released from the IRB in the event of such an institution-wide emergency situation.

## Risks, Discomforts, Potential Harms and Monitoring

1. Describe the risks of each research procedure to participants or others. For each identified risk, provide an assessment of the anticipated seriousness and likelihood of the risk. Some examples of possible risks include but are not limited to:

- Physioal risks (e.g. bodily harms or discomforts, side effects, etc.)
- Psychological risks (e.g. emotional, mental, or spiritual harms or discomforts, changes to thoughts, beliefs, or behaviors, etc.)
- Research data risks (e.g. loss of confidentiality and privacy)
- Social or legal risks (e.g. impacts on relationships or reputation, legal or criminal justice actions for self or others, etc.)
- Financial risks (e.g. impacts on income, employability, or insurability, loss of services, etc.)
- Other risks (e.g. unforeseeable risks of experimental procedures, risks related to particular study designs (randomization, washout, placebo, withholding care/services, deception), etc.)

See the help text for additional guidance.

The risks to the participants include:

For those receiving injections, potential adverse reactions as listed in the informed consent. These risks are extrapolated from FDA package labeling in which the route of administration is different from the current use (per-articular versus IV, IM or epidural use). Adverse effects from this injection (it has been used for years by the orthopedic surgeons in this manner) anecdotally is minimal—generally the most common is temporary nerve palsy and this is very rare.

For those NOT receiving injections, reduced postoperative pain control and the need for more narcotic pain medication postoperatively.

There is no way to quantify the risks that we mention in the ICF since several of the drugs are being used off-label and there is no data on adverse effects except from the primary literature. Most studies that have used this type of pain control have reported no adverse effects (from the drugs). The risks noted in the ICF are extrapolated from the oral or IV use.

We have provided a further review of the literature surrounding the use of the periarthicular injections (uploaded documents)

2. Describe how each of the risks/harms/discomforts identified above will be minimized:

A full review of the patient's medical record, including allergies, will be performed to minimize allergic and other adverse drug reactions. The periarthicular injection will be placed in a region away from nerves so as to prevent temporary or permanent weakness/numbness.

In patients who do not receive the periarthicular injection, they will continue to receive other important components of the perioperative multimodal analgesia protocol.

Patients are monitored at least daily by medical staff after undergoing TKR. Nursing protocol monitors pain scores and pain acceptance rates on an hourly basis post-surgically. Any side effects will be noted during this monitoring process. As previously noted, the risks in this study are notably, potential pain by not receiving the per-articular joint injection, since all patients who are NOT enrolled in the study will likely receive the injection.

3. Describe any potential risks or harms to a community or a specific population based on study findings (e.g. information that could be stigmatizing or derogatory):

None

4. Where appropriate, discuss provisions for ensuring necessary medical, professional, or psychological intervention in the event of adverse events to the subjects:

If there is any adverse reaction to the injection this will be handled by the orthopedic physicians who are caring for the patient during their surgery.

5. Describe criteria for when the investigator would withdraw an individual participant from the study; such as safety or toxicity concerns, emotional distress, inability to comply with the protocol, etc.:

If there is a toxicity or adverse reaction concern, the patient will be withdrawn from data collection and treated appropriately according to current medical guidelines and standards.

Any toxicity event or adverse effects will be managed with the use of fluids, and medications such as anti-emetics. Patient level of monitoring may be increased to allow for closer observation and treatment. Other treatment interventions will be managed with additional interventions as deemed necessary by the treating physicians.

6. Summarize any pre-specified criteria that would trigger the investigator/sponsor/monitoring committee to stop or change the study protocol due to safety concerns:

NA

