## Study Procedures

1. **Describe the study hypothesis and/or research questions. Use lay language whenever possible.**  
The study hypothesizes that those receiving intrathecal Duramorph and local periarthicular injections will have reduced narcotic use when compared with intrathecal Duramorph alone at 48 hours postoperatively.

2. **Describe the study's specific aims or goals. Use lay language whenever possible.**  
The study will assess and compare postoperative pain control in patients receiving intrathecal morphine with and without local periarthicular injections.

3. **Choose all types of recruitment materials that may be used and upload them below:**

- E-mail invitations
- Phone Solicitation scripts (i.e. cold calls or random-digit-dialing)
- Flyers, Mailed Letters or Newspaper/TV/Radio Ads
- TelegRAM announcements
- Website text
- Study-specific web sites (provide the design and text)
- Social Media
- EPIC MyChart Patient Portal research study descriptions
- Psychology Research Participant Pool (SONA) study descriptions
- Scripts for announcements made to groups
- Other recruitment material
- No recruitment materials

4. **Describe the study procedures/methods for identifying and recruiting participants. Address the following three aspects of recruitment in your response.**

1. **Identification of potentially eligible participants or secondary data/specimens of interest.**

- What database(s) will be queried to identify secondary data/specimens
- How potential participants' contact information will be obtained

2. **Recruitment procedures to invite participation in the study (when applicable):**

- How each of the written or verbal recruitment materials and reminders (selected above) will be used
- Who will contact or respond to potential participants
- Locations where recruitment procedures will take place
- The timing and frequency of recruitment attempts

3. **Eligibility screening prior to consent and how those activities will be carried out (when applicable)**

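### A toxicity or adverse reaction concern ends data collection for a randomised patient, although 48-hour opioid use could still be read from the chart

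*Combined protocol and SAP*

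**What the plan says.** In Risks, Discomforts, Potential Harms and Monitoring, question 5 asks when an investigator would withdraw a participant. The answer is: "If there is a toxicity or adverse reaction concern, the patient will be withdrawn from data collection and treated appropriately". No severity grade, attribution or time window is attached, although Collection and Reporting of SAEs and AEs defines both a severity scale and an attribution scale.

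The timing of the trigger can be read in two ways. Question 4 says of a reaction to the injection that "this will be handled by the orthopedic physicians who are caring for the patient during their surgery", which suggests intraoperative events. The second paragraph of question 5 is wider: "Any toxicity event or adverse effects will be managed with the use of fluids, and medications such as anti-emetics". It also allows closer monitoring, so postoperative events fit it as well.

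The hypothesis (Study Procedures, question 1) is "reduced narcotic use when compared with intrathecal Duramorph alone at 48 hours postoperatively". Secondary Data/Specimen Details states: "The data being collected includes pain medicine administered for the first 48 hours after surgery". The last answer under Privacy says that this information comes from later chart review and that care after the operation is standard. Under Randomization, the active arm receives one injection of ropivacaine, clonidine, ketorolac and epinephrine. For the control arm: "The patients in the placebo group will receive 100 mL of 0.9% saline".

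**The concern.** There is no ongoing study drug to stop after a single intraoperative injection. What question 5 withdraws is the patient's data, and a reaction does not by itself prevent 48-hour medication from being read in the chart. The rule thus makes outcome data missing by design, because of an event after randomisation.

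Losses may differ by arm. The risks answer links adverse reactions to the active injection ("For those receiving injections, potential adverse reactions as listed in the informed consent") and greater narcotic need to its absence. The consequence depends on how the trigger is read:

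- **Intraoperative only.** The trigger precedes postoperative opioid use. Bias arises only if withdrawn patients later use more or less opioid than those kept.
- **Postoperative as well.** The expected-event list includes nausea, sedation and pruritus. These can plausibly also follow opioid use, which would tie withdrawal to the outcome itself.

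If the active arm loses more patients and they are heavier opioid users, the benefit is overstated. If the placebo arm loses more of them, it is understated. Blinding does not prevent this, because the event is the trigger.

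**Working it through.** **Inputs from the documents.** 64 patients per arm (Study Procedures, Enrollment) and one injection per patient. No adverse event rate and no SD of opioid use are given, so every loss rate and every link to opioid use below is an assumption. The plan's own calculation of 64 per group concerns pain score up to about 12 hours. It cannot be reproduced, because no mean, SD or test is stated, and it is not used here beyond the arm size.

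**Identity.** Let p be the share of an arm withdrawn and d the mean opioid use of withdrawn minus kept patients, in SD units. The kept mean differs from the full-arm mean by −p × d, so

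bias (active − placebo) = −(pA × dA − pP × dP).

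The standard error with 64 per arm is √(2/64) = 0.177 SD.

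**Intraoperative reading.**

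- d = 0: no bias at any loss rate.
- One patient of 64 in one arm, d = 1: 1/64 = 0.016 SD.
- Two patients of 64, d = 1: 2/64 = 0.031 SD.

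**Postoperative reading, no true effect.** Opioid use is taken as normal with SD 1. P(withdrawn) = expit(a + ln(OR) × opioid use), where OR is the odds ratio of withdrawal per SD and a is solved for each loss rate. Type I error comes from the noncentral t, two-sided 5%, with 64 × (1 − p) kept per arm and the kept patients' variance.

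Worked case, OR 2.72, 3% placebo and 10% active: integration gives dP = 0.961 and dA = 0.908, so the bias is −(0.10 × 0.908 − 0.03 × 0.961) = −(0.0908 − 0.0288) = −0.062 SD.

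| Loss, placebo / active | OR 1.5 | OR 2 | OR 2.72 |
|---|---|---|---|
| 1% / 1% | 0 (5.0%) | 0 (5.0%) | 0 (5.0%) |
| 1% / 3% | −0.008 (5.0%) | −0.014 (5.1%) | −0.019 (5.1%) |
| 2% / 5% | −0.012 (5.1%) | −0.020 (5.1%) | −0.028 (5.3%) |
| 3% / 10% | −0.028 (5.3%) | −0.046 (5.7%) | −0.062 (6.4%) |

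Cells show bias in SD, with type I error in brackets. Negative values are a false benefit, and reversing the loss rates reverses the sign. A simulation of 100,000 trials at OR 2.72 gave −0.019, −0.028 and −0.061 SD, with type I errors of 4.9%, 5.2% and 6.4%.

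**Same mechanism in both arms, true benefit present (OR 2.72).** Heavier users are removed from both arms, and more of them from placebo, so the estimate shrinks:

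| Placebo loss | True benefit 0.3 SD | True benefit 0.8 SD |
|---|---|---|
| 1% | 0.8% | 0.7% |
| 3% | 2.3% | 1.9% |
| 5% | 3.6% | 3.0% |
| 10% | 6.4% | 5.4% |

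**The case against.** The strongest objection is weight. The documents describe the risk as very low and report no attributable events in 15 years of use. At 1% against 3% loss the type I error is at most 5.1%, and nothing in the documents supports a gap as wide as 3% against 10%. This largely stands: the likely effect is small. It is not a firm bound, however. The 15-year record concerns events attributed to the injection, while question 5 asks only for a concern, and the same risks section says the risks cannot be quantified.

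Second, the harmful reading may not be the intended one. Question 4 points to surgery, and AEs of every grade are reviewed through the admission, which sits badly with ending data collection over nausea. This is a fair reading, but question 5 does not limit itself to it. The link between listed events and opioid use is also an inference; the documents list those events under the injected drugs.

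Third, an analysis-set rule may exist in text not available here, because the methods break off at the heading "Preoperative Intervention". That stands, so the absence of such a rule is not counted as a defect. Data Analysis Plans covers only interim analysis, AE review and stopping rules. An analysis rule elsewhere could not in any case restore data that were never collected.

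Fourth, question 5 does not say that data already recorded are deleted, or that the patient leaves the analysis. That is true. But the 48-hour outcome is gathered by later chart review, so a patient withdrawn before then would have no complete value.

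**Conclusion.** The concern holds. Question 5 is an explicit rule with an open-ended trigger. As written, it loses obtainable outcome data on randomised patients, and nothing in the available text repairs it. The direction of bias cannot be settled from the documents.

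The size is close to nil at the expected event rate, and nil if withdrawal is unrelated to later opioid use. It reaches 0.062 SD, with a type I error of 6.4%, only under the assumed 3% against 10% loss and a strong link. The case for change rests on an avoidable exclusion and a very cheap remedy, not on a large expected bias. It should be fixed. Confidence is medium, because the event rates, the link to opioid use and the intended timing of the trigger are all unknown. Loss of safety data is not shown, since AE review continues under the monitoring sections.

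**What to change.** Amend the answer to question 5 along these lines, leaving treatment of the reaction exactly as it is:

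> A toxicity or adverse reaction concern does not end data collection. Pain medicine over 48 hours and AEs continue to be taken from the chart unless the patient withdraws from the study. These patients are included in the opioid comparison in their assigned arm, and the number with such events is reported by arm.

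Opioid use after the event then counts as observed, including use that reflects management of the event. A sensitivity analysis without these patients may be added. One sentence should confirm that this agrees with the continuing AE review in Monitoring Procedures, Collection and Reporting of SAEs and AEs, and Data Analysis Plans.

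The cost is a short amendment to one answer. The medication data are already in the chart, so no visits, staff or patients are added. Two limits apply: the consent wording, not available here, should be checked for consistency, and a patient discharged before 48 hours would have an incomplete chart record under either rule.

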### Data and Safety Monitoring

Data and safety monitoring is a system for checking the study's data at regular intervals over the study period to identify and address issues that could affect the safety of research participants. This requirement is in accordance with 45 CFR 46.111.

The purpose of data and safety monitoring plan is to set forth study team procedures for monitoring/addressing:

- Participant safety (physioal, psychological, etc.)
- Data validity
- Early stopping (termination) based upon changes in risks and benefits.

7. Indicate if this study will have a Data Safety Monitoring Board (DSMB) or a Data Safety Monitoring Plan (DSMP): (Required for all greater than minimal risk studies)

- DSMB
- DSMP
- No DSMB/DSMP (Note: This response is not applicable for greater than minimal risk studies)

8. Describe your Data Safety Monitoring Plan for monitoring the study's data to ensure the safety of participants. This plan should include (but is not limited to) the following elements:

1. Who will monitor data
2. What data and/or processes will be reviewed
3. When and how frequently monitoring will occur
4. What report/documentation will be submitted to the IRB at the time of continuing reviews

See the help text for additional guidance.

The primary objective is to assess and compare postoperative pain control in patients receiving intrathecal morphine with and without a local periarthicular injection.

Opiate requirements postoperatively (morphine equivalents) will be assessed.

